9.7.1.8.4 VITAL SIGNS

Descriptive statistics for vital signs parameters (eg, systolic and diastolic BP, pulse, respiratory rate, temperature, weight) and changes from baseline will be presented by visit and treatment group.

9.7.1.8.5 ELECTROCARDIOGRAMS

For each ECG parameter (including PR interval, RR interval, QRS interval, QT interval, QTc interval (Bazett formula), QTc interval (Fridericia formula), and heart rate), the actual value

and change from baseline will be summarized by visit and treatment group using descriptive statistics.

Shift tables will present changes from baseline in ECG interpretation (categorized as normal; abnormal, not clinically significant; and abnormal, clinically significant) to end of treatment.

Maximum postbaseline QTc (Bazett) and QTc (Fridericia) will also be tabulated by treatment group as follows:

- Number (percentage) of subjects in greater than 450 msec, greater than 480 msec, and greater than 500 msec during the treatment, and
- Number (percentage) of subjects with an increment of greater than 30 msec and greater than 60 msec from the baseline visit.

9.7.1.8.6 OTHER SAFETY ANALYSES

Other safety assessments including adolescent growth evaluations using 95th percentile CDC growth charts and bone age using x-ray of the hand, sexual maturation as measured in Tanner Staging, study drug effect on cognition assessed by Leiter-3, assessment of suicidality using C-SSRS, depression assessment using PHQ-9, will be summarized by treatment group at each scheduled visit. In a subset of subjects, bone mineral density and content, total body fat mass, and total body lean mass using DEXA and their z-score will be summarized by treatment group at baseline and Week 52. For echocardiographic assessments, the proportion of subjects who develop FDA-defined valvulopathy, the proportion of subjects who develop pulmonary hypertension (defined as when a subject's SPAP is ≥ 40 mmHg evaluated by echocardiograph], and change from baseline in SPAP will also be summarized by treatment group at Week 28 and Week 52. (revised per Amendments 01, 03, and 04)

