Population PK/PD modeling will be used to explore the relationship between lorcaserin plasma exposure and response, including but not limited to change in BMI from baseline and the probability of achieving at least a 5% and at least a 10% change in BMI from baseline to Week 52. Additionally, exposure-safety relationships for select safety parameters may be explored graphically depending on the data at the end of study. Any emergent relationship may be modeled as appropriate. Any parameters based on the study data may be considered for exploratory assessment for its relationship to PK.

Pharmacogenomic/Pharmacogenetic Analyses

Not applicable

Safety Analyses

Evaluations of safety will be performed on the Safety Analysis Set. Safety assessments including the incidence of AEs (including changes from baseline in physical examination, neuromuscular sign assessment for serotonin syndrome, and signs and symptoms of priapism and hyperprolactinemia), out-of-normal-range laboratory safety test values, change from baseline in laboratory safety test values, ECGs, vital sign measurements, bone mineral density and content, total body fat mass and total body lean mass by DEXA, FDA-defined valvulopathy, and pulmonary hypertension assessed by echocardiograph will be summarized by treatment group using descriptive statistics or frequency count as appropriate.

No hypothesis testing will be performed for the safety assessment. (Revised per Amendment 04)

Other Safety Analyses

In addition, cognition will be evaluated by the Leiter-3, depression will be evaluated by the PHQ-9, and suicidal ideation and behavior will be evaluated by the C-SSRS, and will also be summarized by treatment group using descriptive statistics or frequency count as appropriate. For echocardiographic assessments, the proportion of subjects who develop FDA-defined valvulopathy, the proportion of subjects who develop pulmonary hypertension [pulmonary hypertension is defined when the subject's systolic pulmonary artery pressure (SPAP) ≥ 40 mmHg evaluated by echocardiograph], and change from baseline in SPAP will be summarized by treatment group at Week 28 and Week 52 using descriptive statistics or frequency count as appropriate. (revised per Amendment 01)

No hypothesis testing will be performed for the safety assessment.

Study Day 1 for all safety analyses will be defined as the date of the first dose of study drug.

Interim Analyses

Not applicable

Sample Size Rationale

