- To assess the safety of Belviq XR, including the effects on cognition by Leiter-3 International Performance Scale (Leiter-3), depression with the Patient Health Questionnaire (PHQ-9), signal of suicidal ideation or behavior with the Columbia-Suicide Severity Rating Scale (C-SSRS), growth measured by CDC growth chart, sexual maturation (pubescence) measured by Tanner Staging scores, and other growth and development parameters by measuring sex hormones, thyroid function, adrenal function, bone age, and biochemical markers of bone health, bone mineral density and content, total body fat mass and total body lean mass by DEXA in a subset of subjects (selected prior to randomization at selected sites), valvular function, pulmonary arterial pressure. (revised per Amendments 01 and 03)
- To assess the pharmacokinetic (PK) of lorcaserin using population PK modeling
- To assess relationships between plasma exposure to lorcaserin and pharmacodynamic (PD) parameters including but not limited to reduction from baseline in BMI and probability of achieving at least a 5% and at least a 10% reduction in BMI from baseline at Week 52 using population PK/ PD modeling

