9.5.1.5.10 OTHER SAFETY ASSESSMENTS

Leiter-3

The Leiter International Performance Scale–Third Edition (Leiter-3) is widely used non verbal measure of intelligence, memory, and attention in those between the ages of 3 and 75 years. The Attention/Memory Battery consists of 5 subtests: 2 measure nonverbal attention; 2 measure memory; and 1 measures cognitive interference (nonverbal Stroop test). These subtests are combined to produce a Memory and Processing Speed composite scores, normalized to a mean of 100 and standard deviation of 15. The Leiter-3 will be used to assess lorcasein effects on cognition, specifically, attention and memory. In addition, signs and symptoms of cognition-related AEs, including impairments in attention, memory, and adverse effects on schoolwork will be captured in the eCRF. (revised per Amendment 01)

PHQ-9

The PHQ-9 is a multipurpose instrument for screening, diagnosing, monitoring and measuring the severity of depression:

- The PHQ-9 incorporates Diagnostic and Statistical Manual of Mental Disorders, 4th Edition (DSM-IV) depression diagnostic criteria with other leading major depressive symptoms into a brief self-report tool.
- The tool rates the frequency of the symptoms which factors into the scoring severity index.
- Question 9 on the PHQ-9 screens for the presence and duration of suicide ideation.
- A follow-up, non-scored question on the PHQ-9 assigns weight to the degree to which depressive problems have affected the subject's level of function.

C-SSRS

The C-SSRS collects information pertinent to suicidal ideation and actions. It consists of a Baseline version which will be administered at Baseline and a Since Last Visit version which will be administered at the remaining visits. C-SSRS will be used to assess signal of depression and suicidal ideation or behavior. Qualified personnel must evaluate positive responses on the C-SSRS and take appropriate action as detailed in the training and

certification process for administering the C-SSRS. It will be performed at Screening and at study visits as designated in the Schedule of Procedures/Assessments (Table 2). (revised per Amendment 01)

DEXA for the Assessment of Bone Mineral Density

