9.7.1.8 Safety Analyses

Evaluations of safety will be performed on the Safety Analysis Set. Safety assessments including the incidence of AEs (including changes from baseline in physical examination, neuromuscular sign assessment for serotonin syndrome, and signs and symptoms of priapism and hyperprolactinemia), out-of-normal-range laboratory safety test values, change from baseline in laboratory safety test values, ECGs, vital sign measurements, bone mineral density and content, total body fat mass and total body lean mass by DEXA, FDA-defined valvulopathy, and pulmonary hypertension by echocardiograph will be summarized by treatment group using descriptive statistics or frequency count as appropriate. (revised per Amendments 01, 03, and 04)

No hypothesis testing will be performed for the safety assessment.

Study Day 1 for all safety analyses will be defined as the date of the first dose of study drug.

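### The Leiter-3 drug effect on cognition is planned only as by-arm descriptive summaries, with no change from baseline and no between-arm difference or interval; a baseline-adjusted contrast should be added

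*Protocol*

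**What the plan says.** Section 8.2 of the protocol lists among the other secondary objectives: "To assess the safety of Belviq XR, including the effects on cognition by Leiter-3". Section 9.5.1.5.10 says the instrument is there to assess "effects on cognition, specifically, attention and memory", and that its Memory and Processing Speed composites are "normalized to a mean of 100 and standard deviation of 15". Table 2 in section 9.5.2.1 schedules it at baseline, at Weeks 5, 28, 52 and 56, and at early discontinuation.

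The analysis is stated in section 9.7.1.8.6: "study drug effect on cognition assessed by Leiter-3, assessment of suicidality using C-SSRS, depression assessment using PHQ-9, will be summarized by treatment group", visit by visit. Under Other Safety Analyses, the Synopsis says the Leiter-3, PHQ-9 and C-SSRS results will be "summarized by treatment group using descriptive statistics or frequency count as appropriate". Section 9.7.1.8 adds: "No hypothesis testing will be performed for the safety assessment".

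Neighbouring measures are specified more fully. Change from baseline is named for laboratory values (9.7.1.8.3), vital signs (9.7.1.8.4) and ECG parameters (9.7.1.8.5). It is also named in the same paragraph as the Leiter-3: "change from baseline in SPAP will also be summarized by treatment group at Week 28 and Week 52". It is not named for the Leiter-3 or the PHQ-9.

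**The concern.** The sentence in 9.7.1.8.6 calls its output a drug effect. In a randomised trial that effect is the contrast between arms, best measured here as the difference in change from baseline. The stated analysis stops at two columns of summaries per visit.

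The Leiter-3 is given up to five times on schedule over 56 weeks, so scores may move in both arms through retesting. The placebo arm is what separates that movement from a drug effect. A table that leaves the subtraction to the reader, without change scores and without an interval, answers the stated objective less precisely than the collected data allow. At stake is whether the report can say how large a cognitive difference between the arms is compatible with the data.

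**Working it through.** **Inputs from the protocol**
- Norm SD of the Leiter-3 composites: 15 (9.5.1.5.10).
- 130 subjects per arm and 40% dropout (9.7.2): 130 × 0.6 = 78 per arm at Week 52.
- The target of 80% with a primary-endpoint assessment (9.5.1.3), if it carried over to the Leiter-3: 130 × 0.8 = 104 per arm.

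**Assumption not in the documents:** test-retest correlation r from baseline to Week 52, taken as 0.7, 0.8 and 0.9. SD 15 is the norm value and is used at both times; it is not an SD expected in this sample.

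**The plan's own figures.** The protocol gives no precision figure for the Leiter-3. Its only power figures concern BMI, and they reproduce at 78 per arm. A difference of 1 kg/m² with SD 2.2 gives 81.0% (normal) or 80.5% (noncentral t), against the stated 80% or more. Rates of 20% against 40% give 78.4%, against the stated figure above 78%. This confirms 78 per arm as the protocol's own planning number.

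**What a reader can build from by-arm means and SDs at Week 52**

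Half-width = 1.96 × SD × √(2/n) = 1.96 × 15 × √(2/78) = 4.71 points (4.74 with the t quantile), which is 4.71/15 = 0.31 SD.

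**What a baseline-adjusted contrast would give**

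Residual SD = 15 × √(1 − r²); half-width = 1.96 × residual SD × √(2/n).

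| r | Residual SD | 78 per arm | 104 per arm |
|---|---|---|---|
| 0.7 | 10.71 | ±3.36 | ±2.91 |
| 0.8 | 9.00 | ±2.82 | ±2.45 |
| 0.9 | 6.54 | ±2.05 | ±1.78 |

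At 78 per arm the range is 3.36/15 = 0.22 SD down to 2.05/15 = 0.14 SD. Simple change scores without adjustment have SD 15 × √(2(1 − r)). They give ±4.7 at r = 0.5, ±3.7 at r = 0.7 and ±3.0 at r = 0.8 (78 per arm).

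**Why by-visit summaries cannot supply the tighter interval.** The variance of within-subject change is s₀² + s₅₂² − 2·r·s₀·s₅₂. By-visit tables give s₀ and s₅₂ but not r, so neither the SD of change nor the adjusted interval can be rebuilt. The visit means also rest on different subjects: about 130 per arm at baseline and 78 at Week 52 under the planning dropout. Subtracting one mean from the other therefore mixes change with who left.

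**Reading the half-widths.** They are not excludable deficits. If the estimate were −2 points with half-width 2.82, the lower limit would be −2 − 2.82 = −4.82, and only larger deficits would be excluded.

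**The case against.** The strongest reply is that descriptive by-arm safety tables without tests are conventional, and that a difference column with an interval is often settled in the SAP. Sections 9.7, 9.7.1 and 9.7.4 defer further detail to that document, and estimation is nowhere ruled out. This stands in part: the protocol is neither wrong nor self-contradictory here, and the SAP may already contain the contrast. What remains is that 9.7.1.8.6 states an analysis of its own, with no deferral in that section, and an SAP that followed it to the letter would contain no contrast.

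The second reply is that cognition is watched in other ways. Under 9.5.1.5.1 investigators review each Leiter-3 result for adverse events and ask about attention and memory at each visit. Cognition-related adverse events are recorded, and a Data Monitoring Committee sees unblinded safety data. This stands as protection of individual subjects, but it does not estimate a mean difference between arms.

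Three stronger readings are tempting, and the documents do not support them:
- A reader might infer that the drug effect can never be estimated. The by-arm n, mean and SD that descriptive statistics normally include give an unadjusted difference, and the protocol bans tests, not estimates.
- A reader might infer that a deficit is hidden if both arms improve on retesting. The placebo summaries at the same visits show the retest gain, and a smaller gain on drug would be visible against it. Maturation is a weaker argument still: the scores are normed, and if the norms are age-specific, which the protocol does not say, part of it is already removed.
- A reader might extend the point to SPAP and DEXA. Change from baseline is already named for SPAP. For DEXA, section 9.5.1.5.10 requires only a minimum of 30 subjects, about 15 per arm before dropout.

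**Conclusion.** The point holds as a worthwhile, inexpensive improvement. For a named safety objective, the protocol plans only by-arm, by-visit Leiter-3 summaries, with neither change from baseline nor a between-arm difference with an interval. The loss is one of precision and of within-subject comparison, not of the contrast itself. A reader could form a crude Week 52 interval of about ±4.7 points, where a baseline-adjusted one would be about ±3.4 to ±2.1.

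These figures rest on the norm SD of 15, on 78 per arm, and on correlations of 0.7 to 0.9 that the documents do not give. More subjects may be retained, because section 9.5.5 keeps those who stop study drug in all assessments. A reader might take the half-widths to mean that the trial could exclude deficits of 2 to 3.5 points. That would hold only if the estimate were near zero and the correlations were as assumed.

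**What to change.** In section 9.7.1.8.6 and under Other Safety Analyses in the Synopsis, add a sentence to this effect: for the Leiter-3 memory and processing-speed composites, the between-arm difference in change from baseline at Weeks 28 and 52 will be reported with a 95% confidence interval from a model with baseline score, sex and age; these intervals are descriptive and no p-value will be given. Keep the statement in 9.7.1.8 that safety data are not tested, since an interval labelled in this way is compatible with it. The same may be done for the PHQ-9 total score.

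No new data or visits are needed; the cost is one model per composite and an added column in existing tables. The downside is a few intervals that are not adjusted for multiplicity, which the descriptive label should make plain.

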9.7.2 Determination of Sample Size

The proposed sample size is based on the comparison of the primary efficacy endpoint, change from baseline in BMI at Week 52 between the Belviq XR 20-mg treatment group and placebo group. Assuming a SD of 2.2 kg/m² and a 40% dropout rate, a sample size of 260 subjects in a 1:1 ratio (n=130 in the Belviq XR 20-mg treatment group; n=130 in the placebo group) will have at least 80% power to detect a treatment difference of 1 kg/m² in BMI, using a 2-sided t-test with $\alpha=0.05$. Assuming the proportion of subjects achieving at least a 5% BMI reduction at Week 52 is 20% for the placebo group and a 40% dropout rate, this sample of 260 subjects (130 subjects for Belviq XR 20 mg and 130 subjects for placebo) will also have greater than 78% power to detect an absolute difference of 20% between the Belviq XR 20-mg group and placebo group, using a 2-sided Chi-Square test with $\alpha=0.05$. The assumption used in the sample size calculation is based on the 2 pivotal lorcaserin studies, APD356-009 and APD356-011 in obese and overweight non-diabetic adult subjects. (revised per Amendment 02)

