9.7.1.2 Definitions of Analysis Sets

- The Safety Analysis Set is the group of subjects who received at least 1 dose of study drug and had at least 1 postdose safety assessment.

- The Full Analysis Set (FAS) is the group of all randomized subjects regardless of adherence to study drug.
- Per-Protocol Analysis Set (PP) is the group of all randomized subjects who are 80% or greater compliant with study medication, completed the study, have no major protocol deviations, have no violations of inclusion or exclusion criteria, and have BMI data at baseline and Week 52. The determination of subjects to be excluded from this population based on the above criteria and list of major protocol violations will be included in the SAP and finalized before data base lock.
- The PD Analysis Set is the group of subjects who had sufficient PD data to derive at least 1 PD parameter.
- The PK Analysis Set is the group of all randomized subjects from whom at least 1 valid lorcaserin plasma concentration was obtained with associated documented dosing history.
- The population PK/PD set is the group of randomized subjects with PK information and who have at least 1 adequately documented measurement of BMI.

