9.7.1.6 Efficacy Analyses

The FAS will be used as the primary analysis set for all efficacy analyses, while the PP will be used as a supportive analysis. Unless specified otherwise, a 2-sided $\alpha=0.05$ significance level will be used for all efficacy analyses.

Primary Efficacy Analysis

The primary efficacy endpoint is the change in BMI from baseline to Week 52. The change from baseline in BMI will be analyzed using analysis of covariance model (ANCOVA) with factors of treatment, sex (male and female) as fixed effect, and the baseline age and BMI as covariates. The missing values will be imputed using a pattern mixture model utilizing multiple imputation (MI) assuming the missing values are missing not at random (MNAR). The missing values will be imputed at each visit using all available values including the retrieved measurement from the postdiscontinuation data. The details of the analysis model and missing value imputation method will be further described in the SAP.

In addition, the following analyses will also be considered as sensitivity analyses:

- PP analysis: The same primary efficacy analyses described above will be repeated based on the PP.
- Change from baseline in standardized BMI score (Z-score): The same primary efficacy analyses described above will be repeated using Z-score.

Subgroup analyses and additional sensitivity analyses, if appropriate, may also be performed and will be described in the SAP.

Key Secondary Efficacy Analysis

The key secondary efficacy endpoint is the proportion of subjects achieving at least a 5% BMI reduction at Week 52. The secondary efficacy endpoint will be analyzed only if the test for the primary efficacy endpoint is statistically significant.

The proportion of subjects achieving at least a 5% BMI reduction at Week 52 will be analyzed using a logistic regression model with factors of treatment, and sex (male and female), and baseline BMI as a covariate using FAS. Subjects with any missing assessment at Week 52 will be considered as treatment failures in this analysis.

Other Secondary Efficacy Analyses

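### The stated power of more than 78% for the key secondary endpoint comes from a completers-only test; the planned missing-equals-failure analysis gives about 71% on the same assumptions

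*Protocol*

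**What the plan says.** Section 9.7.2 fixes "a sample size of 260 subjects in a 1:1 ratio (n=130 in the Belviq XR 20-mg treatment group; n=130 in the placebo group"). For the key secondary endpoint it assumes a Week 52 responder proportion of "20% for the placebo group and a 40% dropout rate", and states that the trial "will also have greater than 78% power to detect an absolute difference of 20" percentage points with a two-sided chi-square test at 0.05. The synopsis (Sample Size Rationale) repeats the statement.

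Section 9.7.1.6 plans a logistic regression for this endpoint with treatment, sex "and baseline BMI as a covariate using FAS". It adds: "Subjects with any missing assessment at Week 52 will be considered as treatment failures in this analysis". Section 9.7.1.2 defines the set: "The Full Analysis Set (FAS) is the group of all randomized subjects regardless of adherence to study drug".

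Sections 9.1 and 9.5.5 keep subjects who stop study drug under follow-up. Section 9.5.1.3 aims for at least 80% of randomized subjects to have the primary endpoint assessed.

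**The concern.** The power statement and the analysis treat the same 40% dropout in incompatible ways. The first takes dropouts out of the denominator and leaves the responder rates at 20% and 40%. The second keeps them in the denominator as non-responders, which leaves 130 per arm but shrinks both proportions and the difference between them. Both rules are fixed in the protocol, so this is not a detail deferred to the SAP.

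The endpoint matters. It is the only key secondary and is tested only if the primary is significant. Section 7.1.2 says the adult indication was awarded on a categorical responder criterion, although that criterion concerns adult body weight and the same section notes that no specific adolescent guidance exists. Readers judging the chance of a responder claim will rely on the stated figure.

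**Working it through.** **Inputs.** From Section 9.7.2: 130 per arm, placebo responders 20%, difference 20 points (so 40% on active), dropout 40%, chi-square test, two-sided alpha 0.05. From Sections 9.7.1.6 and 9.7.1.2: all randomized subjects analysed, missing Week 52 counted as failure. From Section 9.5.1.3: target of at most 20% missing.

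**Formula.** Normal approximation to the chi-square test with n per arm and mean proportion p̄ = (p₁ + p₂)/2:

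power = Φ{ [ (p₂ − p₁) − 1.96·√(2p̄(1 − p̄)/n) ] / √( p₁(1 − p₁)/n + p₂(1 − p₂)/n ) }

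**Step 1: reproduce the stated figure.** n = 130 × (1 − 0.40) = 78, p₁ = 0.20, p₂ = 0.40, p̄ = 0.30. The null standard error is 0.0734 and the alternative standard error 0.0716. Power = Φ[(0.20 − 1.96 × 0.0734)/0.0716] = Φ(0.78) = 78.4%; exact enumeration gives 78.9%. This matches the claim of more than 78%.

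**Step 2: the planned analysis on the same assumptions.** n = 130. With the 40% counted as failures, p₁ = 0.20 × 0.60 = 0.12 and p₂ = 0.40 × 0.60 = 0.24, so the difference is 12 points. With p̄ = 0.18 the standard errors are 0.0477 and 0.0471. Power = Φ[(0.12 − 1.96 × 0.0477)/0.0471] = Φ(0.57) = 71.4%; exact enumeration gives 71.9%. Other approximations give 72.2% (unpooled variance), 72.3% (arcsine) and 65.6% (continuity-corrected).

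**Step 3: other readings of the inputs**, all with 130 per arm and missing counted as failure:

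| Reading | Placebo vs active | Power |
|---|---|---|
| 40% missing, 20%/40% among those observed | 12% vs 24% | 71.4% |
| 20%/40% are already all-randomized rates | 20% vs 40% | 94.5% |
| 30% missing, observed subjects respond at 20%/40% | 14% vs 28% | 79.5% |
| 20% missing, retrieved off-drug subjects respond like completers | 16% vs 32% | 86.0% |
| 20% missing, retrieved off-drug active subjects respond at the placebo rate | 16% vs 28% | 64.8% |

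In the last row the active proportion is 0.60 × 0.40 + 0.20 × 0.20 = 0.28. The response rates of retrieved subjects in the last two rows are assumptions; the protocol gives none.

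**Step 4: what 78% would require.** Under the failure rule with observed rates of 20% and 40%, power is 78.0% at about 32% missing. At 40% missing, it needs an active rate of about 41.9% among observed subjects, or 152 per arm (160 per arm for 80%).

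**Step 5: the primary endpoint.** With 78 per arm, SD 2.2 and a difference of 1 kg/m², power is 81.0% by normal approximation and 80.5% by t-test. The claim of at least 80% holds.

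**The case against.** The best defence has three parts.

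First, the sum is not wrong: the stated figure reproduces, and it is an inequality. If 20% and 40% are all-randomized rates, true power is about 94% and a claim of more than 78% is conservative. Section 9.7.2 does not say which kind of rate it means. This stands as a criticism of the text's clarity, but it does not rescue the sentence. The 78% arises only by cutting n to 78, and that cut has no place if the rates already count dropouts as failures.

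Second, dropout from drug is not the same as a missing Week 52 BMI. The protocol follows subjects after they stop drug and targets at least 80% assessed, and at 20% missing the failure rule can give 86%. This also stands, and it makes 71% conditional. But the power statement itself uses 40%, the 80% is a target, and power at 20% missing falls to 65% if retrieved off-drug active subjects respond at the placebo rate. The roughly 32% missing that would give 78% appears nowhere in the document.

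Third, the sample size is driven by the primary endpoint, so no analysis, error rate or subject is affected. That is correct, and it limits the finding to the stated power of one endpoint.

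**Conclusion.** The power statement for the key secondary endpoint is wrong as written. It gives the power of a completers-only comparison that the protocol does not plan. On the protocol's own inputs the planned analysis has about 71% power, and the expected difference in the analysed proportions is 12 points, not 20.

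The 71% rests on three assumptions:

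- The 20% and 40% are rates among subjects with Week 52 data, which is what the cut to 78 per arm implies.
- The 40% dropout means no Week 52 BMI, equally in both arms. Imbalance matters a good deal: 45% missing on active with 35% on placebo gives about 48%, and the reverse gives about 88%.
- A chi-square test stands in for the planned logistic regression, as in the protocol's own calculation.

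The sample size of 260 and the primary power claim are not in question.

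**What to change.** Keep 260 subjects. In Section 9.7.2 and the synopsis, say that the 20% and 40% are rates among subjects with a Week 52 BMI, and replace the key secondary power sentence with one for the planned analysis. For example: with the 40% who lack a Week 52 BMI counted as failures, the expected proportions are 12% and 24% of 130 per arm, giving about 71% power at a two-sided 0.05 level. Beside it, show the 20%-missing scenarios (about 65% to 86%) and label the assumed response of retrieved off-drug subjects as an assumption.

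A small clarification fits the same edit: in Section 9.7.1.6, make the failure rule depend on a missing Week 52 BMI rather than on any missing assessment. Read literally, the present wording fails a subject who has a valid Week 52 BMI but missed some other test. The power finding does not depend on this change.

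The cost is two short text changes for the power statement, one for the optional clarification, and a less favourable published figure. No additional subjects and no change to alpha are needed.
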